4.2 Exclusion Criteria

201. Diagnosis of leukemia, non-Hodgkin's lymphoma, Hodgkin's disease, or other hematologic malignancy.
202. Radiotherapy to the bone marrow within 6 weeks prior to enrollment OR within 3 months prior to enrollment if prior radiotherapy to the craniospinal axis or to at

- least 60% of the pelvis was received; within 2 weeks prior to enrollment if local palliative radiotherapy was received.
- 203.
204. Primary ocular or mucosal melanoma.
206. History of other malignancy within the past 5 years with the following exception:
- malignancy treated with curative intent and with no known active disease present and has not received chemotherapy for > 5 years before enrollment and felt to be at low risk for recurrence by the treating physician.
207. History or evidence of active autoimmune disease that requires systemic treatment (ie, with use of disease modifying agents, corticosteroids or immunosuppressive drugs). Replacement therapy (eg, thyroxine, insulin, or physiologic corticosteroid replacement therapy for adrenal or pituitary insufficiency, etc.) is not considered a form of systemic treatment.
209. Active herpetic skin lesions or prior complications of herpetic infection (eg, herpetic keratitis or encephalitis).
210. Prior treatment with talimogene laherparepvec or any other oncolytic virus.
211. Prior treatment with a tumor vaccine.
212. Requires intermittent or chronic treatment with an antiherpetic drug (eg, acyclovir), other than intermittent topical use.
- 214.
- 215.
216. Expected to require other cancer therapy while on study with the exception of local palliative radiation treatment.
217. Has acute or chronic active hepatitis B virus or hepatitis C virus infection or received treatment with nucleotide analogs such as those used in the treatment of hepatitis B virus (eg, lamivudine, adefovir, tenofovir, telbivudine, and entecavir), ribavirin, or interferon alpha within 12 weeks of initiation of study treatment.
218. Known or suspected human immunodeficiency virus (HIV) infection.
219. Received live vaccine within 28 days prior to enrollment.
220. No antiplatelet or anticoagulation medications allowed within 7 days prior to talimogene laherparepvec injection except low-dose heparin needed to maintain venous catheter patency.
221. Female subject is pregnant or breast-feeding, or planning to become pregnant during study treatment and through 3 months after the last dose of talimogene laherparepvec.
222. Female subject of childbearing potential who is unwilling to use acceptable method(s) of effective contraception during study treatment and through 3 months after the last dose of talimogene laherparepvec. Note: Acceptable methods of effective contraception are defined in the informed consent/assent form. Where required by local laws and regulations, additional country-specific contraception requirements may be outlined in a country-specific protocol supplement at the end of the Appendix Section of protocol.

Approved

224. Subject has known sensitivity to any of the products or components to be administered during dosing.
225. Subject likely to not be available to complete all protocol-required study visits or procedures, and/or to comply with all required study procedures to the best of the subject and investigator's knowledge.
226. History or evidence of any psychiatric disorder, substance abuse or any other clinically significant disorder, condition or disease (with the exception of those outlined above) that, in the opinion of the investigator or Amgen physician, if consulted, would pose a risk to subject safety or interfere with the study evaluation, procedures or completion.
227. Subject who is unwilling to minimize exposure with his/her blood or other body fluids to individuals who are at higher risks for HSV-1 induced complications (immunosuppressed individuals, HIV-positive individuals, pregnant women, or children under the age of 1 year) during talimogene laherparepvec treatment and through 28 days after the last dose of talimogene laherparepvec.
228. Evidence of clinically significant immunosuppression such as the following:
- primary immunodeficiency state such as severe combined immunodeficiency disease
 - concurrent opportunistic infection
 - receiving systemic immunosuppressive therapy (> 2 weeks prior to enrollment), including oral steroid doses (with the exception of maintenance physiologic replacement). Subjects who require intermittent use of steroids for inhalation or local steroid injection will not be excluded from the study
 - less than 6 months from autologous bone marrow transplant or stem cell infusion
 - history of allogeneic bone marrow transplant
230. History or evidence of xeroderma pigmentosum.
231. Sexually active subjects and their partners unwilling to use a male or female latex condom to avoid potential viral transmission during sexual contact while on treatment and within 30 days after treatment with talimogene laherparepvec. For those with latex allergies, polyurethane condoms may be used.
232. Prior chemotherapy, treatment dose radiotherapy, or biological cancer therapy within 14 days prior to enrollment or has not recovered to Common Terminology Criteria for Adverse Events version 4.0 (CTCAE) grade 1 or better from adverse event due to cancer therapy administered more than 14 days prior to enrollment.
233. CNS tumor or clinically active brain metastases (**patient with a history of treated brain metastases are eligible if there is radiographic evidence of improvement upon the completion of CNS-directed therapy and no evidence of interim progression between the completion of CNS-directed therapy and the screening radiographic study**).
234. Currently receiving treatment in another investigational device or drug study, or less than **14** days since ending treatment on another investigational device or drug study(ies) **or has not recovered to CTCAE version 4.0 grade 1 or better from adverse event due to other investigational device or drug study administered more than 14 days prior to enrollment**. Other investigational procedures while participating in this study are excluded.

Approved

235. Major surgery \leq 14 days prior to enrollment **or has not recovered to CTCAE version 4.0 grade 1 or better from adverse event due to surgery performed more than 14 days prior to enrollment.**

5. SUBJECT ENROLLMENT

Before subjects begin participation in any study-specific activities/procedures, Amgen requires a copy of the site's written institutional review board/independent ethics committee (IRB/IEC) approval of the protocol, informed consent/assent form, and all other subject information and/or recruitment material, if applicable (see [Section 11.2](#)). All subjects or legally acceptable representatives must sign and date the IRB/IEC and Amgen approved informed consent (and assent, if appropriate) form before commencement of study-specific activities/procedures.

A subject is considered enrolled when the investigator decides that the subject has met all eligibility criteria. The investigator is to document this decision and date in the subject's medical record and in/on the enrollment CRF.

Each subject who enters into the screening period for the study (defined when the subject or legally acceptable representative signs the informed consent/assent) receives a unique subject identification number before any study-related activities/procedures are performed. The subject identification number will be assigned by the interactive response **technology (IRT)**. This number will be used to identify the subject throughout the clinical study and must be used on all study documentation related to that subject. Subjects who are determined not eligible after screening must be screen-failed in the **IRT** system and the reason for the screen-failure provided. Subjects who do not meet all eligibility criteria may be rescreened 1 time at the discretion of the investigator. If a subject is being rescreened, he or she may need to re-consent to the study to ensure that the IRB/IEC approved main informed consent/assent form is signed within 28 days of enrollment. Subjects who are determined not eligible after rescreen must be screen-failed in the **IRT** system and the reason for the screen-failure provided. Subjects may only be enrolled once into this study.

The subject identification number must remain constant throughout the entire clinical study; it must not be changed after initial assignment, including if a subject is rescreened.

5.1 Treatment Assignment

All subjects enrolled in the study will be assigned open-label talimogene laherparepvec. The treatment assignment date is to be documented in the subject's medical record and on the enrollment CRF.

6. TREATMENT PROCEDURES

6.1 Classification of Product(s) and/or Medical Device(s)

The Amgen Investigational Product used in this study includes: talimogene laherparepvec.

The Investigational Product Instruction Manual (IPIM), a document external to this protocol, contains detailed information regarding the storage, preparation, destruction, and administration of talimogene laherparepvec.

6.2 Investigational Product

6.2.1 Amgen Investigational Product (Talimogene Laherparepvec)

Talimogene laherparepvec will be manufactured and packaged by Amgen Inc. and distributed using Amgen clinical study drug distribution procedures. Talimogene laherparepvec is supplied as a sterile frozen liquid in a single-use 2-cc Crystal Zenith vial with a gray Fluorotec[®]-coated chlorobutyl elastomer stopper, aluminum seal, and polypropylene cap. Each vial contains a minimum of 1.0 mL talimogene laherparepvec at either 10⁶ PFU/mL or 10⁸ PFU/mL concentrations. The supply for the 10⁶ PFU/mL concentration will be packaged separately from the supply for the 10⁸ PFU/mL concentration.

6.2.1.1 Dosage, Administration, and Schedule

Talimogene laherparepvec must be prepared and administered by a qualified healthcare professional. Subjects should be assessed clinically for adverse events/toxicity prior to each dose using the CTCAE version 4 ([Appendix A](#)). Complete blood count with differential and chemistry panels including liver function laboratory tests (ALT, AST, and total bilirubin) should be obtained according to the Schedule of Assessments ([Table 3](#)) and the results should be checked before each treatment. Dosing will occur only if these test values are acceptable per [Section 6.2.1.2](#) and [6.2.1.3](#). Sedation can be used and the type and dose is up to the discretion of the investigator taking into consideration the subject's medical history, age, and site of disease. Additionally, use of pain medication (eg, acetaminophen/paracetamol/narcotic) or anti-anxiety medication (eg, benzodiazepine) as premedication to help decrease the pain or anxiety associated with the injection is acceptable and left to the discretion of the investigator. Because

flu-like symptoms are common adverse events experienced by HSV-seronegative subjects after talimogene laherparepvec treatment, premedication with the appropriate antipyretic and/or antiemetic medications prior to each talimogene laherparepvec treatment is strongly recommended to prevent the occurrence of these symptoms in the HSV-seronegative subjects. The type and dose will be up to the discretion of the investigator taking into consideration the subject's medical history and age.

Talimogene laherparepvec will be administered by intralesional injection only into injectable cutaneous, subcutaneous, nodal tumors, and other non-visceral tumors with or without image guidance. Talimogene laherparepvec must not be administered into tumor lesions in visceral organs.

The first dose of talimogene laherparepvec will be up to 4.0 mL of 10^6 PFU/mL administered on day 1. The second injection, up to 4.0 mL of 10^8 PFU/mL (or up to 4.0 mL of 10^6 PFU/mL for a dose de-escalated cohort), will be administered 21 (+ 3) days after the initial injection (ie, no sooner than day 22 but should not be delayed more than 3 days after the 21-day time point). All subsequent injections, up to 4.0 mL of 10^8 PFU/mL (or up to 4.0 mL of 10^6 PFU/mL for a dose de-escalated cohort), will be administered every 14 (\pm 3) days. The treatment cycle interval may be increased due to toxicity.

The maximum volume of talimogene laherparepvec administered at any dose is 4.0 mL for any individual lesion and in any treatment.

The recommended volume of talimogene laherparepvec to be injected into the tumor(s) is dependent on the size of the tumor(s) and should be determined according to the injection volume guideline in [Table 2](#). It is recommended that each lesion should receive the maximum amount possible to inject due to tumor properties at each visit before moving on to the next lesion, using the prioritization model below and the injection volume guideline based on tumor size per [Table 2](#). The lesion site injected will be recorded on the CRF.

Approved

Table 2. Talimogene Laherparepvec Injection Volume Guideline Based on Tumor Size

Tumor Size (longest dimension)	Maximum Injection Volume
> 5.0 cm	4.0 mL
> 2.5 cm to 5.0 cm	2.0 mL
> 1.5 cm to 2.5 cm	1.0 mL
> 0.5 cm to 1.5 cm	0.5 mL
≤ 0.5 cm	0.1 mL

On each treatment day, prioritization of injections is recommended as follows:

1. any new injectable tumor that appeared since the last injection
2. by tumor size, beginning with the largest tumor
3. any tumor previously seen on tumor assessment that was too small to inject that has now become large enough to inject

Subjects will be treated with talimogene laherparepvec until subjects have achieved a complete response (CR), all injectable tumors have disappeared, confirmed progressive disease (PD) per modified irRC-RECIST, intolerance of study treatment, 24 months from the date of the first dose of talimogene laherparepvec, or need for alternative anti-cancer therapy, whichever occurs first. Due to the mechanism of action, subjects may experience growth in existing tumors or the appearance of new tumors prior to maximal clinical benefit of talimogene laherparepvec. Therefore, modified irRC-RECIST will be used instead of standard RECIST 1.1 ([Nishino et al, 2014](#)). Details can be found in [Appendix D](#).

The dose (total volume and concentration), lesion site, treatment start date, and lot number of talimogene laherparepvec are to be recorded on the CRF.

6.2.1.2 Dose-cohort Study De-escalation and Stopping Rules

Unlike conventional treatments, talimogene laherparepvec is administered directly into tumors and the dose is dependent on tumor size rather than subject's age, weight or body surface area. As the adult doses were safe and well-tolerated, this phase 1 study is designed with a dose de-escalation schema, which is described in detail in [Section 3.1 Study Design](#).

If the DLT is a serious herpetic event (eg, encephalitis, encephalomyelitis, or disseminated herpetic-like infection) caused by talimogene laherparepvec as

demonstrated by real-time polymerase chain reaction (qPCR) analysis, then the study will be terminated.

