The recommended adult talimogene laherparepvec dose of 10^6 PFU/mL followed by 10^8 PFU/mL 3 weeks later has been shown to be well tolerated in HSV-1 seropositive and seronegative adult subjects. Symptoms of pyrexia, chills and influenza-like illness occurred more frequently during the first 3 months of treatment, particularly in patients who were HSV-1 negative at baseline (Andtbacka et al, 2015). Given this finding, preemptive measures are strongly recommended prior to each talimogene laherparepvec dose to prevent the occurrence of the influenza-like symptoms in the pediatric subjects who might be more susceptible for developing these adverse events.

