6.2.1.2.1 Rules for DLT Evaluation

The DLT evaluation period is 35 days from the initial administration of talimogene laherparepvec. For a subject to be considered DLT-evaluable, subjects must receive 2 doses of talimogene laherparepvec (one dose of up to 4.0 mL of 10^6 PFU/mL followed by a dose of up to 4.0 mL of 10^8 PFU/mL for Dose Level 1, or 2 doses of up to 4.0 mL of 10^6 PFU/mL for Dose Level -1) during the 35 day DLT evaluation period, with the exception when a DLT occurs after the first dose. Subjects may be replaced in a cohort if they are not evaluable for DLT (ie, a subject did not receive at least 2 treatments of talimogene laherparepvec, or ended the study treatment before completion of DLT evaluation period for a reason other than experiencing a DLT).

A DLRT will review the safety data to evaluate possible drug effects and DLT. The DLRT will review the safety data of the first 3 DLT-evaluable subjects in the older age cohort (A1 or A2) to decide if the younger age cohort can be opened for enrollment. The decision to open the younger age cohort for subject enrollment will be based on < 33% DLT rate of the first 3 DLT-evaluable subjects in the older age cohort (A1 or A2) during the DLT evaluation period.

If a DLT occurs in the first 3 DLT-evaluable subjects in the older age cohort (A1 or A2), the younger age cohort will not open until a DLT rate < 33% is observed with at least 6 DLT-evaluable subjects in the older age cohort (A1 or A2). The starting dose for the younger age cohort will be Dose Level 1 (if the DLT rate in the older age cohort at Dose Level 1 is < 33%) or Dose Level -1 (if Dose Level 1 is intolerable for the older age cohort). After both cohorts are open, the DLRT will review the safety data after the earlier of the following events: (a) the addition of 3 new DLT-evaluable subjects in a cohort **until there're 9 DLT-evaluable subjects in the cohort**; (b) a DLT rate \geq 33% considering all DLT-evaluable subjects in a cohort; (c) at the occurrence of the first DLT in either cohort. **If deemed necessary, ad-hoc meetings to review the safety data can be convened anytime by the DLRT.**

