6.2.1.2.3 Definition of DLT

All toxicities will be graded using the CTCAE version 4.0 ([Appendix A](#)).

The occurrence of any of the following toxicities during the DLT evaluation period will be considered a DLT, if judged by the investigator to be related to the administration of talimogene laherparepvec:

- Grade 4 non-hematologic toxicity
- Grade 3 non-hematologic toxicity lasting > 3 days despite optimal supportive care
 - grade 3 fatigue will not be classified as DLT, irrespective of duration
- Any grade 3 or higher non-hematologic laboratory value if:
 - medical intervention is required, or
 - the abnormality leads to hospitalization, or

- the abnormality persists for > 1 week unless deemed not clinically important per both investigator and sponsor.
- Febrile neutropenia grade 3 or grade 4
- Thrombocytopenia < 25 x 10⁹/L associated with bleeding event requiring intervention
- Serious herpetic event:
 - herpetic encephalitis or disseminated herpetic infection
- Grade 5 toxicity (ie, death)
- Any other intolerable toxicity leading to permanent discontinuation of talimogene laherparepvec

If a subject experiences a DLT during the DLT evaluation period, study treatments will be discontinued for that subject.

Subjects who are in CR and no longer have injectable lesions will enter the 30-day safety follow-up and continue to have tumor assessments every 12 weeks for up to 24 months. Subjects who develop a new injectable lesion(s) within 12 months from the start date of treatment, but after all other injectable lesions have responded such that they are no longer injectable are eligible to restart treatment with talimogene laherparepvec under this protocol for up to a further 12 months. This includes subjects that achieve a CR and then develop a new injectable lesion.

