- The subject, for any reason, requires treatment with another anticancer therapeutic agent for the study disease (other than the exceptions noted in [Section 6.4](#)). In this case, discontinuation from the study treatment occurs immediately upon introduction of the new agent.
- Confirmed PD occurs as defined per modified irRC-RECIST or clinical progression per the investigator.
- A grade 2 or greater immune-mediated adverse event (with the exception of vitiligo) or allergic reactions attributed to talimogene laherparepvec that would require a dose delay of greater than 6 weeks from the date of the planned dose.
 - NOTE: immune-mediated glomerulonephritis, vasculitis, and pneumonitis and exacerbation of psoriasis have been observed in subjects receiving talimogene laherparepvec in clinical trials. Most of these subjects had a history of other autoimmune disease and/or prior treatment with agents that offered plausible alternative etiologies; however, immune-mediated adverse events can potentially involve any organ system.
- Any other talimogene laherparepvec-related non-hematologic or hematologic toxicities grade 3 or greater that, in the opinion of the investigator, would require a dose delay of greater than 6 weeks from the date of the planned dose.
- The subject develops clinical evidence of any systemic herpetic infection (such as encephalitis or disseminated infection).

Approved

- An FCBP subject becomes pregnant or fails to use acceptable method(s) of effective contraception.
- A female subject breastfeeds while on study treatment.
- Concurrent medical illness that, in the judgment of the investigator, would make continued treatment with talimogene laherparepvec dangerous for the subject.
- Subject or legally acceptable representative withdraws consent/assent or wishes to stop the study treatment.

For additional information related to special warnings and precautions for the use of talimogene laherparepvec please refer to the latest version of the [talimogene laherparepvec Investigator's Brochure](#).

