10.3.2 Dose Level Review Team (DLRT)

An interim safety analysis is planned after the first 3 DLT-evaluable subjects for each cohort. A DLRT consisting of the Amgen study team, including at least 1 medical monitor, 1 safety representative, and 1 biostatistician, and at least 1 participating investigator who has recruited subjects into this study, will review the safety data to evaluate possible DLTs.

Based on the DLT evaluation rules in [Section 6.2.1.2](#), the DLRT will recommend whether to continue the dose for 3 additional DLT-evaluable subjects in the cohort and if applicable, whether the younger age cohort can be opened for enrollment. Subsequent safety analyses are planned for: (a) every addition of 3 new DLT-evaluable subjects in a cohort **until there are 9 DLT-evaluable subjects in the cohort**; (b) if there have been

≥ 33% DLT rate in the cohort since the last safety analysis; (c) at the occurrence of the first DLT in either cohort. Based on the DLT evaluation rules and safety analyses, the DLRT will make recommendation on dose de-escalation, enrollment halt, the opening or re-opening of the cohort(s) for enrollment and/or the starting dose for the cohort(s). **If deemed necessary, ad-hoc meetings to review the safety data can be convened anytime by the DLRT.**

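### After Day 35, a virus-confirmed serious herpetic event or a treatment-related death requires no study-level step, although dosing may run to 24 months

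*Protocol*

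**What the plan says.** **Study termination.** Protocol Section 6.2.1.2 reads: "If the DLT is a serious herpetic event (eg, encephalitis, encephalomyelitis, or disseminated herpetic-like infection) caused by talimogene laherparepvec", with qPCR as the proof, "then the study will be terminated".

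**What counts as a DLT.** Section 6.2.1.2.3 states: "The occurrence of any of the following toxicities during the DLT evaluation period will be considered a DLT". The list includes serious herpetic events and grade 5 toxicity, if the investigator judges them related. Section 6.2.1.2.1 fixes the window: "The DLT evaluation period is 35 days from the initial administration of talimogene laherparepvec".

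**Length of treatment.** Section 6.2.1.1 allows dosing for up to 24 months from first dose. Section 3.5.1 anticipates 9 months.

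**DLRT reviews.** Sections 6.2.1.2.1 and 10.3.2 require a review after the first 3 DLT-evaluable subjects. Once both cohorts are open there are three triggers: (a) each 3 further evaluable subjects, until a cohort has 9; (b) a DLT rate of 33% or more; and (c) "at the occurrence of the first DLT in either cohort". The DLRT may also meet ad hoc if it sees a need.

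**Single subject.** Section 6.2.1.3 stops treatment permanently, with no time limit, if "The subject develops clinical evidence of any systemic herpetic infection (such as encephalitis or disseminated infection".

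SAP Section 8 adds no stopping rule and refers back to protocol Section 10.3.2.

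**The concern.** A serious herpetic event caused by the product is the only toxicity for which the protocol prescribes ending the study. The rule already demands proof of causation by qPCR, and nothing in the documents explains why the same proof would have no prescribed study-level consequence once the DLT window has closed. The authors did foresee late herpetic infection, because the single-subject rule covers it at any time. They wrote no study-level counterpart.

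At stake is whether other children, including those aged 2 to under 12 years, go on being enrolled and dosed after a late case or a late related death without any body being obliged to look at it first. Section 2.3 describes this as the first use of the product in children with these tumors.

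**Working it through.** **1. The plan's own figure.** Table 5 (protocol Section 10.2; Table 2 in the SAP) gives the chance of declaring a cohort safe with 6 evaluable subjects. Safe means at most 1 DLT, so P(safe) = (1 − p)^6 + 6p(1 − p)^5:

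- p = 10%: 0.531 + 0.354 = 0.886 (stated 89%)
- p = 30%: 0.118 + 0.303 = 0.420 (stated 42%)
- p = 50%: 7/64 = 0.109 (stated 11%)

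The figures reproduce and are not in dispute. They count only DLTs, so they say nothing about events after Day 35.

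**2. One event, two dates.** Take a related, qPCR-confirmed serious herpetic event on Day 34 and again on Day 60. These days lie inside and outside the window however Day 36 is counted.

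| Provision | Day 34 | Day 60 |
|---|---|---|
| Termination of the study (6.2.1.2) | Mandatory | Does not apply |
| Trigger (c), first DLT | Review mandatory, if it is the first | Does not apply |
| Trigger (b), DLT rate of 33% or more | Event counts | Event does not count |
| DLT rate used to declare the dose safe (6.2.1.2.1) | Event counts | Event does not count |
| First-3 review and trigger (a), up to 9 evaluable | Event seen if a review falls due | Same |
| That subject stops treatment (6.2.1.3) | Mandatory | Mandatory |
| Report to the sponsor within 24 hours (9.2.2.2) | Mandatory | Mandatory |
| Ad hoc DLRT meeting, DLRT finding that enrollment is unsafe, sponsor termination (6.2.1.2.1, 10.3.2, 12.1) | Discretionary | Discretionary |

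For a related death, the Day 34 event is a DLT and feeds triggers (b) and (c). On Day 60 only the report within 24 hours is mandatory.

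**3. How far trigger (a) reaches.** Cohort A1 may dose up to 18 subjects (Section 3.1), and trigger (a) ends at 9 evaluable. If the first 9 dosed were all evaluable, 18 − 9 = 9 further subjects could be dosed with no accrual-based review. The Amendment 3 rationale reports 10 subjects enrolled in A1 and 1 in B1, and expects most later enrollment in A1. It does not say how many were evaluable. If 9 or 10 of the 10 were, trigger (a) had already ended in A1; if fewer, at least one such review remained. B1 has no required sample size (Section 10.2), so it may never reach a review set by subject count.

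**4. The judgement-based rules.** Section 6.2.1.2.2 lets the DLRT call a dose intolerable, but words this as being within the DLT evaluation period. Section 6.2.1.2.1 lets it find continued enrollment unsafe with no such limit. Neither obliges it to meet because a late event has occurred.

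**The case against.** The best defense is that the design is coherent. Fixed rules are tied to the DLT window, where the primary endpoint is measured, and later events are left to judgement. The sections on termination, DLT definition and single-subject discontinuation can all be followed together. Serious events reach the sponsor within 24 hours and go on to regulators, investigators and ethics committees as required. The DLRT weighs all available data across cohorts, can meet at any time and can find enrollment unsafe. The sponsor can end the study at any time. Amendment 3 added ad hoc meetings with safety need in mind.

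Much of this stands, and it rules out several stronger readings that a reader might infer:

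- **That every DLRT trigger depends on a DLT.** It does not. The first-3 review and trigger (a) depend on subject counts and cover safety data generally, so a late event could surface there.
- **That no study-level action could follow a late event.** It could. What is missing is an obligation.
- **That the share of doses given after Day 35 measures the risk.** Nothing in the documents ties serious herpetic events to cumulative dosing. The window is also not strictly two doses: the third is nominally due on Day 36 but, with the 3-day allowance, can fall on Day 33.
- **That the protocol identifies a longer herpetic risk period.** Section 2.4 says that certain symptoms "occurred more frequently during the first 3 months of treatment", but these are pyrexia, chills and influenza-like illness.
- **That the termination rule was meant to apply at any time.** Section 6.2.1.3 speaks of a DLT arising during the DLT evaluation period, which might suggest that DLTs can also arise later. The definition in Section 6.2.1.2.3 does not allow that.

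The defense does not show that the 35-day limit on the termination rule was intended. Nor does it replace a required review with anything firmer than an optional one.

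**Conclusion.** The point holds as a gap in mandatory oversight, not as an absence of oversight. The termination rule and triggers (b) and (c) cease to apply after 35 days, against an anticipated 9 months and a maximum of 24 months of treatment. Trigger (a) closes the gap only partly and only while a cohort has fewer than 9 evaluable subjects.

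The conclusion rests on reading DLT as Section 6.2.1.2.3 defines it. It assumes nothing about how often such events occur: the documents give no rate for serious herpetic events, and they are presumably rare. The DLT estimate and Table 5 are unaffected. The change should be made because it protects subjects at little cost.

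**What to change.** 1. The sponsor should reconcile Section 6.2.1.2 with Sections 6.2.1.1, 6.2.1.2.3 and 6.2.1.3, and state whether the study-level consequence of a qPCR-confirmed serious herpetic event is meant to end at Day 35 and, if so, why. Which rule should apply after Day 35 is for the sponsor to decide.
2. In Sections 6.2.1.2.1 and 10.3.2, add one mandatory DLRT review: for any treatment-related grade 5 event or any serious herpetic event, regardless of the DLT window and of the 9-subject limit. The decision that follows stays with the DLRT and the sponsor.

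The cost is a few sentences and an occasional extra meeting. The DLRT already exists, and serious events already arrive within 24 hours. Collection covers all serious events up to 30 (+7) days after the last dose, and related ones through long-term follow-up. The SAP needs no change, since it refers to protocol Section 10.3.2.
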